3. LIST OF ABBREVIATIONS AND DEFINITIONS OF TERMS

Table 1: Abbreviations and acronyms

Abbreviation or acronym	Explanation
ADA	Antidrug Antibodies
AE	Adverse Event
ALT	Alanine Aminotransferase
AST	Aspartate Aminotransferase
ATC	Anatomic Therapeutic Class
AUC	The Area Under the Concentration curve
BLQ	Below the Limit of Quantification
BMI	Body Mass Index
CI	Confidence Interval
CL	Apparent clearance
CLDQ	Chronic Liver Disease Questionnaire
Cmax	The maximum serum level observed over the dose interval
CRF	Case Report Form
CS	Clinically Significant
CSR	Clinical Study Report
DDST	Denver II Developmental Screening Test
DNA	Deoxyribonucleic Acid
ECG	Electrocardiogram
eCRF	Electronic Case Report Form
EMA	European Medicines Agency
ERT	Enzyme Replacement Therapy
FACIT	Functional Assessment of Chronic Illness Therapy
FDA	Food and Drug Administration
GGT	Gamma glutamyltransferase
HDL-C	High Density Lipoprotein Cholesterol
HS-CRP	High-Sensitivity C-Reactive Protein
ICH	International Conference on Harmonization
IMP	Investigational Medicinal Product
IAR	Infusion Associated Reaction
INR	International Normalized Ratio
IV	Intravenous
LAL	Lysosomal acid lipase
LDL-C	Low Density Lipoprotein Cholesterol
LLOQ	Low Limit of Quantification
MCS	Mental Component Summary (SF-36)

Abbreviation or acronym	Explanation
MedDRA®	Medical Dictionary for Regulatory Activities
MEGE	Multi-Echo Gradient Echo
MRI	Magnetic Resonance Imaging
NCS	Not Clinically Significant
PedsQL	Pediatric Quality of Life Inventory
PK	Pharmacokinetic
PT	Preferred Term
PT (INR)	Prothrombin Time
PPT (INR)	Partial Thromboplastin Time
QOW	Every other week dosing
QTc	QT-interval for ECG corrected for heart rate
SAE	Serious Adverse Event
SAP	Statistical Analysis Plan
SC	Safety Committee
SFA	Stature-for-Age
SOC	System Organ Class
SOP	Standard Operating Procedure
TEAE	Treatment-Emergent Adverse Event
Tmax	The time to reach the Cmax
UK-MELD	United Kingdom Model for End-Stage Liver Disease
V	Volume of distribution after IV infusion
WFA	Weight-for-Age
WHO	World Health Organization
WHO-DD	World Health Organization Drug Dictionary

4. **Description of the Protocol**

LAL-CL06 is an open-label, multicenter study to evaluate the safety and efficacy of SBC-102 (sebelipase alfa) in a more broad population of subjects with Lysosomal Acid Lipase Deficiency (LAL-D) than have been previously studied.

Following a screening period of up to 45 days, each eligible subject will receive an intravenous (IV) infusion of SBC-102 at an initial dose of 1 mg/kg every other week (qow). A dose escalation to 3 mg/kg qow - and subsequently to 3 mg/kg every week (qw) - may be considered for a subject who satisfies the criteria outlined in Section 6.1 of the study protocol. Each subject will receive up to 96 weeks of treatment, then proceed to an expanded treatment period for a maximum of 48 weeks, after which a follow-up phone call will be conducted to assess adverse events (AEs) and concomitant medications approximately 30 days later.

The primary objective of the study is to evaluate the safety and tolerability of SBC-102 in LAL-D subjects who have not been previously studied.

The secondary objectives are:

- to evaluate effects of SBC-102 relative to Baseline assessment of lipid metabolism and liver abnormalities (including histopathology);
- to evaluate the effects of SBC-102 on additional clinical parameters of LAL-D including those not previously well characterized in the literature;
- to evaluate the effects of SBC-102 on growth parameters in pediatric subjects presenting with evidence of growth delay;
- and to evaluate the immunogenicity of SBC-102.

[figure not shown]
The exploratory objectives are:

- to further characterize the pharmacokinetics (PK) of SBC-102 in pediatric subjects, subjects with severe hepatic dysfunction, and those who have had a previous liver or hematopoietic stem cell transplant;
- and to evaluate the effect of SBC-102 on health-related quality of life (HRQOL) assessments.

An independent program-level safety committee (SC) appointed by the Sponsor will provide additional oversight of subject safety in this study through periodic and ad-hoc reviews of safety data.

A schematic of the study is provided in Figure 1. Further details on target population, inclusion/exclusion criteria, schedule of assessments and study procedures are available in the study protocol.

Figure 1: Study Flow Diagram

^a Each subject will initiate treatment in the open-label extension period (Week 100) at the same dose of sebelipase alpha they received during the last infusion of the treatment period (Week 96), unless criteria for dose modification are met (see Section 6.1 of Study Protocol).

^b Refer to Section 6.1 of Study Protocol for dose escalation criteria.

4.1. Changes from Analyses Specified in the Protocol

The following items are specified in the protocol and are not part of this analysis plan:

- The urinalysis summary of the change from baseline will not be summarized. However urinalysis results will be provided in the subject listings.
- The summary of the change in vital signs during and after infusion relative to pre-infusion values will not be summarized; instead, the change from baseline (defined below) to each post-baseline visit will be summarized. Given that multiple vital sign measurements are taken at each post-baseline visit, the average of the measurements within a visit will be summarized.
- At the time of this Statistical Analysis Plan (SAP) amendment, only 2 subjects have been anti-drug antibody (ADA) positive. As a result, a clarification was added that many of the ADA analyses will only be performed in the event that at least 5 subjects are ADA positive.
- The effect of sebelipase alpha on growth parameters in pediatric subjects will be evaluated among all subjects younger than 18 years old. The protocol specifies analyzing these data conditional on subjects having had manifestations of impaired growth. However, the analysis will not be limited to subjects showing signs of impaired growth.
- The AE table showing the incidence of AEs across time intervals will not be presented.
- The protocol indicates that percentages will be calculated including subjects with missing values.
 However, percentages will be based on subjects with non-missing values unless otherwise specified.

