6.1. Treatment Administered

All eligible subjects will receive repeat IV infusions of sebelipase alfa at an initial dose of $1 \text{ mg}\cdot\text{kg}^{-1}$ qow. Consecutive infusions must be at least 7 days apart. All study infusions will be administered by qualified medical personnel. Up to and including Week 24, study infusions are recommended to be administered over approximately 2 hours. After Week 24, infusions may be administered over approximately 1 hour, as tolerated by the subject (see [Section 6.5.2](#)). Prior to any infusion of sebelipase alfa, the subject will be assessed for signs and symptoms of an acute illness, including but not limited to: vomiting, fever, upper respiratory or gastrointestinal infection. If an acute illness is suspected, it is recommended that the Investigator determine whether to hold the study drug dose for that visit. In case of any questions, the Medical Monitor must be consulted.

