8.7.1. Adverse Events

Adverse events will be coded to system organ class and preferred term using the Medical Dictionary for Regulatory Activities. All AEs, SAEs, and IARs will be listed; separate listings will also be provided for subjects who die while on study and who discontinue the study due to an AE. The number and percentage of subjects experiencing any AE, any related AE, any SAE, any related SAE, and any IAR and, deaths and any other discontinuations due to an AE will be tabulated.

Frequency of treatment-emergent AEs, SAEs, and IARs will be tabulated by preferred term within the system organ class. Frequencies will also be presented by the classifications of severity and causality. In addition, frequency of AEs, SAEs, and IARs will be presented for time periods spanning the entire course of treatment with sebelipase alfa: up to 24 weeks after the first dose, > 24 to 48 weeks, > 48 to 72 weeks, > 72 to 96 weeks. As appropriate, additional listings, summary tables, and graphics will be generated to evaluate IAR frequency and severity over time. The incidence of AEs leading to study discontinuation will be summarized.

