7.2.1. SBC-102 Exposure

Number of weeks in the study and number of study drug infusions received will be summarized overall and; any changes in dose will be described in listings, and may also be provided in tabular summaries.

Exposure to study drug (SBC-102) will be summarized overall doses for the following parameters: the total number of infusions attempted, the number of infusions completed both without and with a rate change or infusion interruption and the number of infusions where the entire infusion volume was not administered will be presented. In addition, a summary will be provided showing the number of weeks on specific doses.

A data listing will be presented, sorted by subject within initial dose of SBC-102, providing the dates, total planned and actual volumes of drug infused, infusion rate and duration of the each infusion along with any modification to the infusion.

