7.2.2.1. Overall Summary of Adverse Events

All TEAEs will be presented using summary statistics (n and n, %), showing the number of events as well as the number and percentage of subjects with the event.

Table 4: Subcategories For Treatment-Emergent Adverse Events (TEAEs)

Relationship
Related AEs
Not Related AEs
Severity
Mild
Moderate
Severe

The relationship between an AE and the study drug will be assessed as: not related; unlikely related; possibly related; or related. Subjects with at least one related AE and subjects with at least one not related AE will be summarized. Related AEs will include those AEs considered 'possibly related' or 'related' by the investigator; and not related AEs will include those AEs considered 'not related' or 'unlikely related'. The severity or intensity of the severity will be assessed and summarized as mild, moderate, or severe.

The number and percentage of subjects with an event meeting these criteria will be summarized according to the most severe occurrence of an AE for summaries of severity or intensity, and the most extreme relationship of the AE for summaries of relationship to study drug. The number of events will be summarized as reported, with no accounting for the most extreme severity or relationship. Additionally, the number and percentage of subjects who withdrew from the study due to an AE or who died on study will be presented along with the number of events meeting each of these criteria. These statistics will be prepared for all TEAEs and, separately, for SAEs and IARs.

7.2.2.2. AEs, SAEs and IARs by System Organ Class (SOC) and Preferred Term (PT)

The frequencies of TEAEs, SAEs, IARs and percentage of subjects with events will be tabulated by PT within SOC. Subjects are counted once in each SOC and PT. Percentages will be based on the total number of subjects in the specific analysis population. SOCs will be listed in order of frequency of occurrence.

Frequencies will also be presented by the classifications of severity and causality (i.e., relationship to study drug). The incidence of AEs leading to study discontinuation and SAEs leading to discontinuation will also be summarized.

A listing of IARs will be presented for those subjects who had a change in dose. This listing will include the subject number, and the prior dose administered, in addition to the standard adverse event listing elements.

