7.12. Subgroup Analyses

Demographic and baseline disease characteristics and efficacy outcomes will be summarized by: age at start of infusion (<12 Years *versus* >=12 Years), gender (Male *versus* Female), baseline use of lipid-lowering medications (Yes *versus* No), genetic mutation category (Homozygous for common mutation *versus* Heterozygous for common mutation *versus* Other mutation), baseline fibrosis or cirrhosis status, and baseline ALT level (<1.5 x ULN vs >=1.5 x ULN). Efficacy outcomes and selected demographic or baseline disease characteristics will also be summarized for subjects 2-4 years old. HRQOL outcomes will not be summarized by subgroup. Adverse event summaries will be presented by age at start of infusion.

Summaries will be provided in the event that at least 5 subjects are included in each subgroup defined by a characteristic (eg. At least 5 subjects with ADA positive and ADA negative).

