9.4.7.1 Treatment-emergent Adverse Events (TEAEs)

Treatment-emergent AEs (TEAEs) are events with start dates and start times on or after the date and time of the first study drug dose (SBC-102). All other AEs are considered Pre-Treatment Adverse Events (PTAEs).

Subject percentages are based on the total number of treated subjects.

The relationship between an AE and the study drug will be classified as: not related; unlikely related; possibly related; or related. AEs assessed as "possibly related" or "related" are further categorized as "Related AEs". AEs assessed as "not related" or "not related" are further categorized as "Unrelated AEs".

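### SAP 4.1 withdraws the protocol's AE table by 24-week period without a reason, and SAP 7.2.2 specifies no tabular summary of when adverse events or infusion reactions occur

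*SAP*

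**What the plan says.** Protocol 8.7.1 commits that "frequency of AEs, SAEs, and IARs will be presented for time periods spanning the entire course of treatment with sebelipase alfa". The periods are up to 24 weeks, >24 to 48, >48 to 72 and >72 to 96. The same section separately promises, as appropriate, listings, tables and graphics on IAR frequency and severity over time.

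SAP 4.1 lists protocol items that are not part of the analysis plan. One bullet reads: "The AE table showing the incidence of AEs across time intervals will not be presented". No reason is attached.

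What the SAP does plan:

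- **7.2.2.1:** an overall summary "showing the number of events as well as the number and percentage of subjects with the event". It adds: "These statistics will be prepared for all TEAEs and, separately, for SAEs and IARs".
- **7.2.2.2:** tables by system organ class and preferred term, severity and causality; full listings; and an extra IAR listing for subjects whose dose changed.
- **7.12:** "Adverse event summaries will be presented by age at start of infusion".
- **9.4.7.1:** "Subject percentages are based on the total number of treated subjects".
- **7.2.1:** "Number of weeks in the study and number of study drug infusions received will be summarized overall".
- **7.14:** two reports, one with data to Week 96 and one with data for the whole study.

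The protocol lets conditions change at two of the dropped cut points. Protocol 6.1: "After Week 24, infusions may be administered over approximately 1 hour, as tolerated by the subject", against about 2 hours before. Protocol 5.7 lets post-infusion monitoring shorten from Week 24, and 6.5.2 permits home infusion after Week 48. Both are conditional.

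**The concern.** Safety is the primary objective (Protocol 2.1), and Protocol 7.1.3 treats IARs as events of special interest. A reader of the study report will want to know whether reactions cluster in the first months, fade, or change once infusions may be shorter, monitoring briefer or the setting the home. The protocol's table was built on 24-week cut points that separate these phases. Without it, every planned AE table pools the whole of treatment, and a pooled percentage mixes risk with length of exposure. The planned exposure data allow a crude overall rate, but that rate says nothing about timing either.

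**Working it through.** **1. Protocol and SAP side by side.**

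| Protocol 8.7.1 | SAP |
|---|---|
| AEs by 24-week period | Withdrawn in 4.1, no reason |
| SAEs and IARs by 24-week period | Not named in the 4.1 bullet; nothing specified in 7.2.2 |
| IAR frequency and severity over time, as appropriate | Not withdrawn in 4.1; nothing specified in 7.2.2 |

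SAP 7.2.2 and 7.12 contain no table indexed by time. The documents give no event rate to reproduce, so the rest is illustration.

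**2. Planned infusions per period.** Every other week from Week 0: Weeks 0 to 24 = 13, then 12 in each later 24-week period; 13 + 12 + 12 + 12 = 49 by Week 96. Weeks 98 to 144 add 24, all beyond the protocol's last period.

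**3. What the pooled table cannot separate.** Assume every subject stays on every-other-week dosing to Week 96, with the same independent IAR risk p per infusion. The whole-period percentage is P = 1 − (1 − p)^49; p = 0.01 gives 0.389. Now let the risk be p1 in the first period and r × p1 afterwards, and solve (1 − p1)^13 × (1 − r·p1)^36 = 1 − P.

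- Constant: first period 1 − 0.99^13 = 0.122; each later period 1 − 0.99^12 = 0.114.
- r = 0.5: p1 = 0.0158, later 0.0079; periods 0.187, then 0.091 each.
- r = 2: p1 = 0.0058, later 0.0115; periods 0.072, then 0.130 each.

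Expected IARs per subject are 0.49 in all three (for r = 0.5: 13 × 0.0158 + 36 × 0.0079 = 0.49), which is 0.49/49 = 1.0 per 100 infusions. So neither the planned percentage nor a crude rate per infusion tells the patterns apart.

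**4. Range of assumed risk** (first v later period):

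| IARs per 100 infusions | Whole period | Constant | Halved | Doubled |
|---|---|---|---|---|
| 0.5 | 22% | 6% v 6% | 10% v 5% | 4% v 7% |
| 1.0 | 39% | 12% v 11% | 19% v 9% | 7% v 13% |
| 2.0 | 63% | 23% v 22% | 34% v 17% | 14% v 24% |

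**5. The plainest case.** Suppose 6 of 30 subjects have an IAR. The pooled table reads 20% (Clopper-Pearson 95% CI 7.7% to 38.6%) whether all six occurred before Week 24 or all after Week 48. A period table with everyone still treated would show 6/30 in one period and 0/30 (0% to 11.6%) in another.

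**6. Denominator.** If 90%, 80% or 70% of treated subjects are still on treatment, a true period risk of 12% shows as 12 × 0.9 = 10.8%, 9.6% or 8.4% when divided by all treated subjects.

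**7. Length of follow-up.** At an assumed 0.5 first events per patient-year, 1 − exp(−0.5 × weeks/52.18) gives 39% at 52 weeks, 60% at 96 and 75% at 144. This supports adding rates; it is a separate matter from the withdrawn table.

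**The case against.** The strongest reply has five parts.

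- **Open declaration.** The departure is stated in the right section, and other bullets there (urinalysis, growth, percentage denominators) also lack a reason. That stands: nothing is concealed, and the missing reason alone would be a small matter. The missing substitute is what counts.
- **Scope of the bullet.** A reader might infer that the SAP expressly cancels the SAE and IAR intervals and leaves event timing nowhere in the report. The text does not go that far. The bullet names only AEs; loss of the other two parts is inferred from silence in 7.2.2. The protocol's IAR-over-time sentence is not withdrawn, only left unspecified. Listings carry dates, Protocol 7.3 records events within 24 hours of infusion by date and time, and comparing the two reports gives one cut at Week 96. None of these is a summary around Week 24 or 48.
- **Oversight.** The Safety Committee reviews aggregated data about every six months, with ad hoc reviews for severe IARs. Subject protection does not depend on this table. But those reviews follow calendar time and are not study-report output.
- **Yield.** At 30 subjects, 19% v 9% is about 6 v 3 subjects (exact 95% CIs 8% to 39% and 2% to 27%). Treating the two counts as independent, the table would fail to show the first period higher about 18% of the time (25% at 20 subjects) under the halved pattern, and fail to show it lower about 30% (37%) under the doubled one. This stands, and it argues for overall counts rather than preferred-term detail. Low precision applies equally to the tables the SAP keeps.
- **Selection.** Weeks 24 and 48 are earliest permitted dates. Shorter infusion depends on tolerance; shorter monitoring and home infusion depend on Sponsor approval and the absence of moderate or severe reactions (for home infusion, within the prior 24 weeks). A reader might take the restored table as a test of those changes. It cannot be one, because each period mixes selected subjects who changed with those who did not.

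**Conclusion.** The gap is real and worth closing. The protocol plans a view of safety over time; the SAP withdraws the AE part without a reason and specifies nothing for SAEs or IARs. The planned tables cannot show whether reactions cluster early or shift after Week 24 or Week 48.

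Its size is moderate. It affects how the primary objective is reported, not any estimate or comparison: the study is single-arm and descriptive, and a claim that the results would be biased is not supported. The percentages above rest on assumed risks that are equal and independent across infusions and subjects, every-other-week dosing and, in steps 3 to 5, no dropout. They show what pooling can hide and are not forecasts. The documentary comparison needs none of these assumptions; only the loss of the SAE and IAR parts is read from silence.

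**What to change.** **Restore.** Delete the 4.1 bullet and add to SAP 7.2.2 one table of overall counts of subjects and events for TEAEs, SAEs and, above all, IARs by 24-week period, not by preferred term. Explaining the deletion in 4.1 would leave the gap open.

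**Improve on the protocol's table.** Use the number still on treatment at the start of each period as denominator. For the final report add >96 to 120 and >120 to 144 weeks.

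**Useful additions, not protocol restorations.** IARs per infusion and events per patient-year, from the exposure data already planned in SAP 7.2.1.

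**Label the table descriptive.** Say that cells are sparse and that the changes allowed from Weeks 24 and 48 are permitted, not automatic, and depend on tolerance or on the absence of recent reactions.

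**Cost.** One table per report and two rate rows, from AE onset dates and infusion records already collected. The downside is thin late periods with wide intervals (4/30: 4% to 31%; 2/20: 1% to 32%), given about 30 subjects in Protocol 8.2 or no more than 20 in SAP 9.3.

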4.2. Changes from Analyses Specified in the Previous Version of the SAP

In addition to items described in Section 4.1, Changes from Analyses Specified in the Protocol, the additions, clarifications and a few deletions have been made to the previous version of the SAP.

The following additional summaries have been described in this version of the SAP:

- Additional baseline characteristics are summarized including, among others, a summary of the LAL enzyme activity and DNA results at baseline.
- The number and percentage of subjects on a modified diet at baseline and with changes in diet over the course of the treatment period are summarized.
- The number of weeks on specific doses of sebelipase alpha is summarized.
- A listing of infusion associated reactions (IARs) for those subjects with a change in sebelipase alpha dosing is added.
- Summaries of select laboratory parameters will be presented relative to the upper limit of normal (ULN).
- The summary of the Child-Pugh Status is described.
- Details of the physical examination summaries are provided.
- A shift from baseline in the interpretation of the 12-lead ECGs has been described.
- The percent change from baseline is added as a summary of each endpoint for which a change from baseline was planned.
- The United Kingdom Model for End-Stage Liver Disease (UK-MELD) summary is described.
- A summary of the post-baseline LAL enzyme activity is described.

The following clarifications have been provided to this version of the SAP:

- Medical histories are summarized separately for those identified as prior and concomitant disease.
- The Denver II assessment will be presented using the overall score and not the domain scores.
- Exploratory analyses of the effect of ADAs on the efficacy of SBC-102 will not be explored using stratified analyses. This may be added if at least 5 subjects are ADA positive at the time of the analysis.
- Laboratory abnormalities will not be specified as CS (Clinically Significant) or NCS (Not-Clinically Significant) by the Investigator or designee; instead, clinically significant changes from a subject's baseline value or previous values are recorded as AEs.
- In the appendices, the scoring of the Functional Assessment of Chronic Illness Therapy (FACIT)-Fatigue was changed to correctly reflect that Items 7 and 8 are not reverse scored, and that the Pediatric Quality of Life Inventory (PedsQL) Total Score and Psychosocial Health Summary Score are not computed if at least 1 scale score is missing.

The following summaries have been removed from this version of the SAP:

- Spaghetti plots of laboratory parameters are replaced with waterfall plots of the percent change from baseline to Week 96. Spaghetti plots may be provided.
- For anthropometric measures in which results are compared to population norms using z-scores and percentiles, only the percentiles will be summarized.

5. **DEFINITIONS**

